4.5 Study Duration

Phase 1: The enrollment period for Phase 1 will last up to 18 months. Subject's participation will last from 1 to 7 days depending on cohort and randomization assignment.

Phase 2: Enrollment period will last up to 24 months. Subject's participation will last from 1 to 7 days depending on cohort and randomization assignment.

The study will be complete when all subjects have been enrolled and all data collected. The study can be terminated at any time, for any reason, by NovaSignal. Should this occur, the study investigator will be notified as soon as possible. The Principle Investigators will be responsible for informing their IRBs of the termination of the trial.

4.6 Phase 1 and 2 Subject Inclusion/Exclusion Criteria

4.6.1 Cohort A LVO

4.6.1.1 Inclusion Criteria

A subject must meet all of the following inclusions criteria to be enrolled in the study:

1. *Subject aged 18 years and older
2. (*) Large vessel occlusion of the intracranial ICA, MCA (M1, M2), or multiple areas of the aforementioned locations confirmed by computed tomography angiography (CTA)

3. Subject or Legally Authorized Representative has the ability to provide informed consent and comply with the protocol.

4.6.1.2 *Exclusion Criteria*

A subject cannot be enrolled in the study if any of the following exclusion criteria are met:

1. (*) Head CT findings consistent with acute primary intracranial hemorrhage (SAH, ICH, etc.)
2. * Hemodynamically unstable patients requiring pharmacological support for hypertension
3. * Subjects who underwent partial or full craniotomy
4. * Additional intracranial pathologies present (tumor, hydrocephalus, etc.)
5. (*) Anticipated insufficient time to acquire a complete initial scan as described by the protocol
6. * Subjects who have a physical limitation preventing placement of the system.

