Study Sponsor: NovaSignal Corp. [name] National Institute of Health (NIH)	Protocol No.: NA-01STR-03 Regulatory Class: II Study Device(s): NovaGuide and/or Lucid TCD System Development Phase: Phase 1: Feasibility; Phase 2: Pivotal
3. Subjects who underwent partial or full craniotomy 4. Additional intracranial pathologies present (tumor, hydrocephalus, etc.) 5. Anticipated insufficient time to acquire a complete initial TCD scan as described by the protocol 6. Subjects who have a physical limitation preventing placement of the system.	
Cohort B Non-LVO	
Inclusion Criteria	
1. Subject aged 18 years and older 2. Non-large vessel occlusion confirmed by computed tomography angiography (CTA) 3. Subject or Legally Authorized Representative has the ability to provide informed consent and comply with the protocol.	
Exclusion Criteria	
1. CTA findings including: a. Occlusions in the common carotid artery, internal carotid artery, anterior carotid artery, middle cerebral artery (M1 and M2 segments), anterior communicating artery, basilar artery, posterior communicating artery and vertebral arteries. 2. Head CT findings consistent with acute primary intracranial hemorrhage (SAH, ICH, etc.) 3. Hemodynamically unstable patients requiring pharmacological support for hypertension 4. Subjects who underwent partial or full craniotomy 5. Anticipated insufficient time to acquire a complete set of scans as described by the protocol 6. Subjects who have a physical limitation preventing placement of the system.	
Phase 2 Study Design	
Phase 2 will include up to 312 subjects (156 cohort A and 156 in cohort B) presenting with stroke like symptoms for which diagnostic imaging has been ordered. Primary and secondary endpoints will be calculated after completion of Phase 2.	

Protocol Synopsis:	
Study Sponsor: NovaSignal Corp. [name] National Institute of Health (NIH)	Protocol No.: NA-01STR-03
	Regulatory Class: II
	Study Device(s): NovaGuide and/or Lucid TCD System
	Development Phase: Phase 1: Feasibility; Phase 2: Pivotal
Imaging Core Lab Analysis: All imaging data will be sent to a core laboratory which will provide independent quantitative and qualitative assessment of all study data. They will be blinded to the study and radiology report data and provide independent review.	

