4.2.2 Phase 2 Study Endpoints

Phase 2 Primary Endpoint:

- Area Under the Curve (AUC), Sensitivity, and Specificity of VCI when compared against standard of care CTA imaging for large vessel occlusion assessment.

Phase 2 Secondary Technical Efficacy Endpoint:

- Area Under the Curve (AUC), Sensitivity, and Specificity of a novel machine learning (ML) algorithm when compared against standard of care CTA imaging for large vessel occlusion assessment.

- VCI and experimental ML algorithm compared to prehospital/neurological clinical scales for alternative diagnostic criteria.

Phase 2 Primary Safety Endpoint:

- Incidence of device-related serious adverse events
- Last Known Normal (LKN) to First Hospital Arrival (Initial Door-In) time
- Door to Initial CT imaging (non-contrast) time
- Door to IV-tPA time
- Door to Initial CTA Acquisition time
- Door to Groin Puncture time
- CTA Acquisition to Groin Puncture time

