4.6.2 Cohort B Non-LVO

4.6.2.1 *Inclusion Criteria*

A subject must meet all of the following inclusions criteria to be enrolled in the study:

1. * Subject aged 18 years and older
2. (*) Non-large vessel occlusion confirmed by computed tomography angiography (CTA)
3. Subject or Legally Authorized Representative has the ability to provide informed consent and comply with the protocol.

4.6.2.2 *Exclusion Criteria*

A subject cannot be enrolled in the study if any of the following exclusion criteria are met:

1. (*) CTA findings including:
 - a. Occlusions in the common carotid artery, internal carotid artery, anterior carotid artery, middle cerebral artery (M1 and M2 segments), anterior communicating artery, basilar artery, posterior communicating artery and vertebral arteries.
2. (*) Head CT findings consistent with acute primary intracranial hemorrhage (SAH, ICH, etc.)
3. * Hemodynamically unstable patients requiring pharmacological support for hypertension
4. * Subjects who underwent partial or full craniotomy
5. (*) Anticipated insufficient time to acquire a complete set of scans as described by the protocol
6. * Subjects who have a physical limitation preventing placement of the system.

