11 STATISTICAL ANALYSIS

11.1 Phase 1 Statistical Analysis:

Primary Endpoint Analysis: Demonstration of VCI diagnostic performance at or exceeding 85% ROC-AUC (targeting SEN greater than 90%) to standard of care imaging.

Biomarker Validation and Analysis: VCI will be computed for each subject according to the procedure outlined in section 3.5, and group differences will be assessed using appropriate statistical methods. ROC-AUC will be computed detailing separability between groups for comparison to standard of care imaging (CTA) and prehospital/neurological clinical scales, along with SEN, SPE, and accuracy at various levels of diagnostic threshold, including that corresponding to Youden's maximal J-statistic.

Sample size calculation: From the results of our feasibility study, we estimate that expected effect size between VCI distributions for LVO (cohort A) and IHC groups (cohort B) will be large (Cohen's $D > 1.25$), such that only a small number of subjects in each group ($N = 11$) will be sufficient to detect significant differences (alpha of 0.05) with standard statistical power of 80%. However, in Phase 1 we seek to demonstrate the stronger aim of biomarker diagnostic performance in excess of 85% ROC-AUC. Assuming this target AUC is met, then sample size determines the confidence bounds on that estimate. In Phase 1 we require a sample of sufficient size to power confidence in the superiority of VCI diagnostic performance relative to current clinical prehospital stroke assessment scales. As existing preclinical scales top out at 78% AUC, this can be accomplished with a sample of roughly 50 subjects in each patient group, which gives a one-tailed 95% confidence bound on the target 85% AUC of less than 7%. The specification of 54 subjects per group is a target number intended to guarantee acquisition of a sufficient sample assuming at least 90% of target enrollment.

Initial safety endpoint analysis: Throughout the study we will collect adverse events, which will be used to determine the safety of the device within the acute stroke environment. In our EXPEDITE study which is also run in the ER for stroke assessment, the device has been designated minimal risk by the IRB and we have not had any serious adverse events in over 80 subjects. We will continue to closely monitor this metric.

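### Other intracranial pathology bars patients from Cohort A but not Cohort B, and no planned analysis separates its influence on AUC, sensitivity and specificity from that of occlusion

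*Combined protocol and SAP*

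**What the plan says.** Eligibility is set separately for each cohort and applies to both phases.

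- **Cohort A (LVO).** Section 4.6.1.2, exclusion 4, bars "Additional intracranial pathologies present (tumor, hydrocephalus, etc".). The synopsis has the same item in the same position: "3. Subjects who underwent partial or full craniotomy 4. Additional intracranial pathologies present (tumor, hydrocephalus, etc".).
- **Cohort B (non-LVO).** The synopsis goes straight from craniotomy to scan time: "4. Subjects who underwent partial or full craniotomy 5. Anticipated insufficient time to acquire a complete set of scans as described by the protocol". Section 4.6.2.2 does the same, with "Subjects who underwent partial or full craniotomy" followed by "Anticipated insufficient time to acquire a complete set of scans as described by the protocol". Inclusion asks only for age, consent and "Non-large vessel occlusion confirmed by computed tomography angiography (CTA"), none of which removes a patient with a tumor or hydrocephalus.
- **Shared exclusions.** Hemorrhage, hemodynamic instability, craniotomy, insufficient time and physical limitation appear in both lists.
- **Primary endpoint (sections 4.2.1 and 4.2.2).** "Area Under the Curve (AUC), Sensitivity, and Specificity of VCI when compared against standard of care CTA imaging for large vessel occlusion assessment".
- **Contrast.** Section 11.1 sizes the study on the difference between the two cohorts: "expected effect size between VCI distributions for LVO (cohort A) and IHC groups (cohort B) will be large".

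**The concern.** Sensitivity is estimated in patients screened free of other intracranial pathology. Specificity is estimated in patients who were not screened for it. If such pathology alters the flow waveform, the separation between cohorts measured by the AUC is partly a product of the entry rule. Section 3.5 describes curvature as responsive to small features of the waveform, so an effect cannot be ruled out, although no section says there is one.

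Either direction is possible. Pathology that makes VCI look like LVO lowers specificity and AUC. Pathology that moves VCI away from LVO values raises them. A threshold chosen at the maximum of Youden's J (section 11.1) would also carry the make-up of Cohort B into the reported sensitivity.

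Nothing else in the plan deals with this. Section 4.9 randomizes TCD against no TCD inside each cohort, so it cannot balance A against B. The subgroup analyses in section 11.2 cover site and age. The data list in section 4.18 has no item for intracranial pathology beyond relevant medical history, so a later sensitivity analysis is not assured.

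**Working it through.** **1. The plan's own precision figure.** The plan names no formula, so I assume the Hanley–McNeil standard error. With AUC = A and n per group, U = A/(2−A), V = 2A²/(1+A), and SE² = [A(1−A) + (n−1)(U−A²) + (n−1)(V−A²)]/n².

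- Phase 2 (section 11.2): A = 0.90, n = 150. U = 0.8182, V = 0.8526, SE = 0.0185. The one-sided 95% half-width is 1.645 × 0.0185 = 0.0304, giving a lower bound of 0.8696. The plan states 3% and 87%.
- Phase 1 (section 11.1): A = 0.85, n = 50. SE = 0.0391 and half-width 0.0642. The plan states less than 7%.

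Both figures reproduce. The eligibility difference does not change them; it concerns what the AUC measures, not how precisely.

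**2. Effect on the AUC.** Let f be the share of Cohort B with additional pathology, AUC_clean the AUC of Cohort A against the rest of Cohort B, and AUC_path the AUC of Cohort A against the affected subjects. The AUC is the probability that a random Cohort A subject ranks as more LVO-like than a random Cohort B subject, so it is an exact mixture:

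AUC = (1−f) × AUC_clean + f × AUC_path

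The documents give neither f nor AUC_path. I take AUC_clean = 0.90 (the Phase 2 target), f from 2% to 10%, and AUC_path from 0.5 (affected subjects indistinguishable from LVO) to 1.0 (perfectly separated). The count is f × 156, the Phase 2 size of Cohort B with TCD.

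| f | Count of 156 | AUC_path = 0.5 | AUC_path = 1.0 |
|---|---|---|---|
| 2% | about 3 | 0.98×0.90 + 0.02×0.5 = 0.892 | 0.98×0.90 + 0.02 = 0.902 |
| 5% | about 8 | 0.95×0.90 + 0.05×0.5 = 0.880 | 0.95×0.90 + 0.05 = 0.905 |
| 10% | about 16 | 0.90×0.90 + 0.10×0.5 = 0.860 | 0.90×0.90 + 0.10 = 0.910 |

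The largest downward shift in this range is 0.40f, which equals the plan's 0.03 half-width at f = 0.03/0.40 = 7.5% (about 12 of 156). The largest upward shift is 0.10f, which reaches 0.03 only at f = 30%.

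**3. Effect on specificity.** Assume a fixed threshold with 90% sensitivity and 90% specificity in unaffected subjects. If affected subjects score like LVO, 10% of them test negative, so specificity = (1−f) × 0.90 + f × 0.10. This gives 88.4%, 86.0% and 82.0% for f = 2%, 5% and 10%. If all affected subjects test negative, it is (1−f) × 0.90 + f, or 90.2%, 90.5% and 91.0%.

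**The case against.** The best defence is realism. Section 2 aims at prehospital LVO identification, and section 4.4 describes Phase 2 patients as presenting with symptoms like those of stroke. Specificity should then hold in non-LVO patients who have another cause for their symptoms, and removing them narrows the control group and could flatter AUC and specificity. The word additional in the Cohort A item may also mean in addition to the occlusion, which would explain why it appears only there. The first argument stands: it counts against simply deleting these subjects from the primary set. It does not justify a one-sided rule, because a realistic population would also include LVO patients with other pathology. The second argument is a guess that the plan does not confirm.

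A reader might infer more than the documents support:

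- *That the cohorts do differ in pathology and the AUC is biased.* The criteria permit such subjects in Cohort B but do not require them. Prior craniotomy, excluded in both cohorts, already removes some. No section states an effect on VCI.
- *That the rule inflates performance.* Direction is unknown, and with a true AUC of 0.90 the upward shift is at most 0.01 at f = 10%. The larger possible shift is downward, which works against the sponsor's target.
- *That an AUC of 0.86 breaches the plan's 87% limit.* That limit is conditional on an observed AUC of 90%. At 0.86 the 90% success criterion has already failed and the limit no longer applies.

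**Conclusion.** The mismatch is real. It appears in the synopsis and again in the main text, so it is not a slip in one place, and it is neither explained nor handled in the analysis. The primary A-against-B measures therefore rest on unequal eligibility, and a reader of the results could not tell whether that mattered.

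The consequence is a possibility, not a demonstrated bias. For 2% to 10% of Cohort B affected, the AUC moves by between −0.04 and +0.01 around 0.90. At 2% the shift is at most 0.008, well inside the plan's own 0.03 bound. These figures rest on assumed prevalence and on AUC_path between 0.5 and 1.0; a value below 0.5 would need affected subjects to look more LVO-like than LVO subjects themselves. This is a low-priority point, worth acting on because the remedy is cheap.

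**What to change.** 1. Reconcile the exclusion lists in sections 4.6.1.2 and 4.6.2.2 and in the synopsis, or state why they differ. Matching can be reached by adding the item to Cohort B or by removing it from Cohort A; the choice depends on the intended population.
2. Add a data field in section 4.18 for additional intracranial pathology, completed for every subject from the non-contrast CT that section 4.15 already schedules in all cohorts.
3. In sections 11.1 and 11.2, prespecify AUC and specificity in two sets: one with the same pathology criterion applied to both cohorts, and one with all Cohort B subjects, so that mimics still count towards a realistic specificity. State which set is primary.

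The cost is one data field and one extra analysis, with a few non-LVO subjects absent from the matched set. The loss of precision is slight. Even if both groups fell from 156 to 140 (a 10% loss), the Phase 2 half-width at AUC 0.90 would go from 0.0298 to 0.0314 by the formula above.

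This does not address the different scan windows: within three hours of CTA and before treatment in Cohort A, against within 24 hours of enrollment in Cohort B. That is a separate difference between the cohorts and needs its own answer.

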4.6.2 Cohort B Non-LVO

4.6.2.1 *Inclusion Criteria*

A subject must meet all of the following inclusions criteria to be enrolled in the study:

1. * Subject aged 18 years and older
2. (*) Non-large vessel occlusion confirmed by computed tomography angiography (CTA)
3. Subject or Legally Authorized Representative has the ability to provide informed consent and comply with the protocol.

4.6.2.2 *Exclusion Criteria*

A subject cannot be enrolled in the study if any of the following exclusion criteria are met:

1. (*) CTA findings including:
 - a. Occlusions in the common carotid artery, internal carotid artery, anterior carotid artery, middle cerebral artery (M1 and M2 segments), anterior communicating artery, basilar artery, posterior communicating artery and vertebral arteries.
2. (*) Head CT findings consistent with acute primary intracranial hemorrhage (SAH, ICH, etc.)
3. * Hemodynamically unstable patients requiring pharmacological support for hypertension
4. * Subjects who underwent partial or full craniotomy
5. (*) Anticipated insufficient time to acquire a complete set of scans as described by the protocol
6. * Subjects who have a physical limitation preventing placement of the system.

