2 BACKGROUND AND RATIONALE OF STUDY

The incidence of Large Vessel Acute Ischemic Stroke (AIS) has been estimated to be approximately 250,000 patients per year in the United States and is the leading cause of disability and fifth leading cause of death. Although endovascular interventions (stentriever) and pharmaceutical (tPA) treatments exist for large vessel occlusion (LVO), their use is limited due to the short time window from symptom onset during which these treatments are indicated to be administered. Moreover, recent estimates suggest only approximately 10% of eligible patients receive interventional treatment which has shown to lead to better outcomes in several world-wide RCTs. Currently, the gold standard for stroke diagnosis is CT angiogram (CTA) which is limited to in-hospital use or a low number of mobile stroke ambulances, all costing multi-millions of dollars, requiring expert operators and IV injection of iodine-rich contrast material. Additionally, the clinical stroke assessment scales (RACE, LAMS, CPSS) used in the field, although low cost and non-invasive, have proven unreliable due to training requirements and low inherent accuracies, with SEN and SPE ranging in a recent study from 0.50-0.64 and 0.83-0.92, respectively[13,14]. In order for intervention to be successful, a standardized, quantitative, field based (prehospital and pre-CTA) diagnostic tool is needed to improve LVO identification and ensure rapid transfer to a capable medical facility.

Goals. Establish clinical viability of a fully automated, non-invasive transcranial Doppler (TCD) derived biomarker based on cerebral hemodynamics for prehospital LVO assessment.

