4.4 Study Population Size

Phase 1: Approximately 108 subjects will be randomized to the TCD only group (54 subjects in Cohort A and 54 subjects in Cohort B). An additional 108 subjects will be randomized to the NO TCD group. An interim feasibility and safety assessment will be completed after Phase 1.

Phase 2: Approximately 312 subjects presenting with stroke like symptoms for which diagnostic imaging has been ordered will be enrolled (156 in Cohort A and 156 in Cohort B). Primary and secondary endpoints will be calculated after completion of Phase 2.

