4.7 Subject Pre-Screening

Subjects will be pre-screened to determine their initial eligibility and interest in a study. Pre-screening criteria indicated with an asterisk * in section 4.6 (Phase 1 & Phase 2) Inclusion/Exclusion imaging criteria are considered standard of care in stroke management. Asterisks in parentheses (*) indicate inclusion/exclusion criteria that can be evaluated at sites that routinely perform multimodal CT or MRI as they are considered standard of care in stroke management. Therefore, subject eligibility to pre-screening criteria can be evaluated without obtaining informed consent. Informed consent will be obtained once subject has satisfied pre-screening criteria. All subjects pre-screened and screened will be documented on the Screening/Enrollment log.

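### Isolated occlusions outside the intracranial ICA, M1 and M2 fit neither cohort, so the accuracy results and the 87% AUC bound cannot be claimed for large vessel occlusion in general

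*Combined protocol and SAP*

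**What the plan says.** Section 4.6.1.1 defines the reference-positive cohort as "Large vessel occlusion of the intracranial ICA, MCA (M1, M2), or multiple areas of the aforementioned locations", confirmed by CTA. Section 4.6.2 defines Cohort B as non-large vessel occlusion on CTA and then excludes "Occlusions in the common carotid artery, internal carotid artery, anterior carotid artery, middle cerebral artery (M1 and M2 segments), anterior communicating artery, basilar artery", followed by "posterior communicating artery and vertebral arteries". The synopsis repeats both lists.

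The claims are worded more widely than these two cohorts:

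- The endpoints in 4.2.1 and 4.2.2 and the success criterion in 11.5 refer to LVO without naming vessels. Section 5.1 asks the Core Lab whether an LVO is present, also without naming them.
- Section 4.4 describes Phase 2 subjects as "presenting with stroke like symptoms for which diagnostic imaging has been ordered".
- Section 2 sets the goal as prehospital LVO assessment and says that a prehospital, pre-CTA "diagnostic tool is needed to improve LVO identification and ensure rapid transfer to a capable medical facility".
- Section 11.2 says that about 150 subjects per group would give 95% confidence that the AUC in the general population is above 87%.

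Section 4.7 adds: "All subjects pre-screened and screened will be documented on the Screening/Enrollment log". No planned output draws on that log to show who fell between the cohorts.

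**The concern.** The two vessel lists are not complements. The patients between them are identified by CTA, which is the test the biomarker is meant to precede. In prehospital use they cannot be set aside, because nobody yet knows that they belong to this group.

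VCI is computed from MCA flow (3.5). A common carotid or extracranial ICA occlusion lies upstream of the MCA, so it could plausibly alter the waveform with no target vessel occluded. A basilar or vertebral occlusion does not lie upstream of the MCA, so an MCA measure might not register it at all. Whether either pattern counts as an error depends on whether the patient is labelled LVO or non-LVO, and the protocol does not give the label.

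What is at stake is the scope of the conclusion. Phase 2 is meant to support a regulatory submission for an expanded indication (section 2), and a result for a selected contrast could be read as a result for suspected LVO.

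**Working it through.** **Step 1. Set the two lists side by side.** The table shows eligibility on vessel criteria alone, for an isolated occlusion.

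| Occluded vessel | Cohort A (4.6.1) | Cohort B (4.6.2) |
|---|---|---|
| Intracranial ICA, M1, M2 | in | excluded |
| Common carotid | not listed | excluded |
| Extracranial ICA | not listed | excluded (any ICA) |
| 'Anterior carotid artery' | not listed | excluded |
| Anterior or posterior communicating | not listed | excluded |
| Basilar, vertebral | not listed | excluded |

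Every row after the first falls in neither cohort. The gap concerns isolated occlusions only: an extracranial ICA occlusion together with an M1 occlusion meets Cohort A's vessel criterion. If 'anterior carotid' means anterior cerebral, an anterior cerebral occlusion is in the gap. If it does not, that vessel is not on the exclusion list.

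**Step 2. Reproduce the plan's own bound.** Inputs from 11.2: AUC A = 0.90, n = 150 per group, one-sided 95% (z = 1.6449). The Hanley-McNeil standard error is

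SE² = [A(1−A) + (n−1)(a−A²) + (n−1)(b−A²)] / n², with a = A/(2−A) = 0.8182 and b = 2A²/(1+A) = 0.8526.

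SE² = (0.09 + 149×0.00818 + 149×0.04263) / 22,500 = 0.0003405, so SE = 0.01845.

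Half-width = 1.6449 × 0.01845 = 0.0304. Lower bound = 0.90 − 0.0304 = 0.8696.

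This matches the stated 3% and 87%; at 156 per group the bound is 0.8702. For Phase 1 (11.1: AUC 0.85, 50 per group), SE = 0.03905 and the half-width is 0.0642, which agrees with the stated figure of less than 7%. The sample size is not at fault. The bound covers sampling error for patients like those enrolled and says nothing about patients who could not be enrolled.

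**Step 3. See what the omitted patients could do.** Let f be their share of the reference class they would join, and x the value of the metric in them. Then

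metric in the wider population = (1−f)×0.90 + f×x.

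For specificity, x = 1 − flag rate; for sensitivity, x is the detection rate; for AUC, x is their AUC against the opposite class. The documents give neither f nor x, so every value below is an assumption.

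| f | x = 0.50 | x = 0.70 | x = 0.90 | x = 0.95 |
|---|---|---|---|---|
| 5% | 0.880 | 0.890 | 0.900 | 0.9025 |
| 10% | 0.860 | 0.880 | 0.900 | 0.905 |
| 20% | 0.820 | 0.860 | 0.900 | 0.910 |

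The range runs from a loss of 8 points to a gain of 1 point. An AUC of 0.90 falls to 0.87 when f = 0.03/(0.90−x): 7.5% at x = 0.50, 10% at x = 0.60, 15% at x = 0.70 and 30% at x = 0.80.

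**Step 4. Direction depends on the label.**

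- Counted as non-LVO and flagged more often than Cohort B: specificity and AUC are optimistic, and sensitivity does not change.
- Counted as LVO and missed more often than Cohort A: sensitivity and AUC are optimistic, and specificity does not change.
- Classified as well as the enrolled patients, or better: nothing is overstated.

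**The case against.** A reader might infer that the design inflates specificity and AUC. The documents do not show that. They contain no prevalence, flag rate or reference label for the omitted patients. A calculation that assumes flag rates above Cohort B's false-positive rate must produce a loss, and one that assumes lower rates must produce a gain. Nor are the cohorts only the easy extremes: Cohort A includes M2 occlusions, and Cohort B's list does not name stenosis, MCA occlusion beyond M2 or posterior cerebral occlusion. These objections stand, and they rule out any statement of bias as fact.

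It can also be said that triage is a future use. Section 2 states that no care decisions rest on study measurements and that Phase 1 will define the context of use; 3.3 says the use is not for diagnosis. Cohort A can be read as an operational definition of LVO, and 11.1 sets the comparison as Cohort A against Cohort B. On that reading, 'general population' in 11.2 means only the population behind the sample. This softens the point but does not remove it. The wider wording is in the protocol's own endpoints, success criterion and confidence statement, and nothing there tells the reader that it carries a vessel restriction.

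Finally, a reader might infer that Cohort B's exclusion should be cut back to the Cohort A vessels. That would place basilar and common carotid occlusions in a cohort defined as non-LVO. It would replace a limit on scope with a doubtful reference label, and the other exclusions would still leave some CTA-read patients in neither cohort.

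**Conclusion.** The gap is real, and nothing else in the documents closes it. The Phase 1 and Phase 2 AUC, sensitivity and specificity apply to intracranial ICA/M1/M2 occlusion versus no occlusion of any vessel in Cohort B exclusion 1. They do not support a claim about LVO in general, or 95% confidence that a general population AUC exceeds 87%. This conclusion rests on the eligibility text alone and needs no assumed figures.

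Accuracy may be optimistic for triage by an unknown amount. The span of 0.82 to 0.91 around 0.90 illustrates sensitivity to the assumed f (5% to 20%) and x (0.50 to 0.95); it is not an estimate. The point should be acted on, because it changes what the trial can conclude.

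**What to change.** 1. In the synopsis, 4.2, 11.1, 11.2 and 11.5, define the target condition as intracranial ICA, M1 or M2 occlusion, and the comparator as no occlusion of any vessel in Cohort B exclusion 1. In 11.2, replace the reference to the general population with the population of patients who meet the two cohorts' criteria.
2. Report from the Screening/Enrollment log, by vessel, how many CTA-read patients fit neither cohort. If a sensitivity range accompanies the count, label its inputs as assumptions, let flag rates run below as well as above the Cohort B false-positive rate, and cover sensitivity and AUC as well as specificity.
3. State which vessel 'anterior carotid artery' means, in both the synopsis and 4.6.2.

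Cohort B exclusion 1 can stay as it is. The cost is a narrower claim and, at most, a vessel or reason field added to a log that is already kept.
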